To address potential for substantial under-estimation of the treatment effect, efficacy analyses will be performed on a final efficacy analysis population as described in Section 7.1. Safety analyses will be performed on the Safety analysis population.

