5 TRIAL OBJECTIVES

The following objectives and associated endpoints are part of this study.

Table 1: Study objectives and associated endpoints.

| Objectives | Endpoints |
|---|--|
| Primary | |
| To characterize safety of study intervention | Through Day 35 
 • Frequencies of grade 3 adverse events (AEs) and grade 4 AEs • AEs resulting in study intervention discontinuation • All SAEs |
| To assess efficacy of study intervention | 
 • Proportion of participants who progress to moderate or severe disease category or higher (Gates MRI ordinal scale ≥ 3) through Day 28 |
| Secondary | |
| To assess clinical efficacy of study intervention | 
 • Time to disease resolution, defined as symptoms resolution only (new onset COVID-19 symptoms resolved, and pre-existing symptoms returned to baseline*) through Day 28 • Time to disease resolution, defined as both viral clearance (two consecutive negative diagnostic tests) and symptoms resolution (new onset COVID-19 symptoms resolved, and pre-existing symptoms returned to baseline*) through Day 28. • Proportion of participants who progress to moderate or severe disease category or higher (Gates MRI ordinal scale ≥ 3) at Days 8, 14 and 21 • Proportion of participants who achieve disease resolution, defined as symptoms resolution only, at Days 8, 14, 21 and 28 • Proportion of participants who achieve disease resolution, defined as both viral clearance and symptoms resolution, at Days 8, 14, 21 and 28 • Gates MRI scale score at Days 8, 14, 21 and 28 • World Health Organization (WHO) ordinal scale score at Days 8, 14, 21 and 28 • Incidence and number of days of hospitalization at Days 8, 14, 21 and 28 |
| Exploratory | |
| To assess virological efficacy | 
 • Quantity (and change from baseline) of SARS CoV-2 virus at Days 8, 14, 21 and 28 |
| To assess viral sequence | 
 • Phylogenetic relationships of SARS-CoV-2 viruses sequenced from positive nasal swab samples |

*Baseline refers to health status prior to contracting new onset COVID-19 symptoms.

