7 STUDY POPULATIONS

7.1 Analysis Populations

An interim analysis was conducted on 28 January, 2021 using the data cut of 8 January, 2021. Efficacy interim analyses were produced based on the first 200 randomized participants who either had discontinued the study or had completed Day 28 in the ITT population. The interim efficacy primary endpoint result will be reported in the CSR using the data cut of 8 January, 2021.

IDMC's recommendation that the clinical study be stopped impacts the efficacy evaluation for the participants who were continuing in the study and had not yet reached Day 21 of the study (end of treatment period) as of 4 February, 2021. In order to have meaningful results of the final efficacy analyses, efficacy analyses will be performed on a final efficacy analysis set of participants who met either one the following criteria:

- Completed or discontinued the study or progressed prior to 5 February, 2021.
- Completed Day 21 or later visits as of 5 February, 2021.

Final analysis will be conducted following database lock.

- Efficacy analyses will be produced for randomized participants who meet the selection criteria described above and also meet the analysis population criteria described below.
- Safety analyses will be produced for all participants in the database who received at least one dose of study intervention.

Table 2: Analysis populations

| Population | Description |
|-------------------|--|
| ITT Population | All participants in the ITT population who met the criteria stated above. Participants will be analyzed according to the intervention to which they were randomized. |
| mITT population | All participants in the ITT population, who received the study intervention and have mild disease at study entry. Participants will be analyzed according to the intervention they actually received. |
| PP population | All participants in the ITT population, who received the study interventions as planned, have mild disease at study entry, and did not substantially deviate from the protocol procedures. Participants will be analyzed according to the intervention they actually received. |
| Safety population | All participants randomly assigned to study intervention, who received the study intervention. Participants will be analyzed according to the intervention they actually received. |

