11.2 Secondary Analysis

Secondary analyses will be conducted in the ITT population. Sensitivity analyses of secondary analyses will be performed using the mITT and PP populations, to assess the robustness of the secondary results.

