| Participant 6 | N | N | Y | Y | N | N | Y | Y | Y | Y | Y | DR at Day 14 |
| Participant 7 | N | N | N | N | N | N | N | N | N | N | Y | DR at Day 28 |
| Participant 8 | N | N | N | N | N | Y | Y | Y | Y | N | N | No DR, censored at Day 28** |
| Participant 9 | N | Y | NA | NA | NA | NA | NA | NA | NA | NA | NA | DR at Day 4 |
| Participant 10 | N | NA | NA | NA | NA | NA | NA | NA | NA | NA | NA | No DR, censored at Day 1 |
| Participant 11 | Y | Y | Y | Y | Y | Y | Y | Y | Y | Y | Y | DR at Day 1 |
| Participant 12 | N | Y | N | N | N | Y | Y | N | Disc. | | | No DR, censored at Day 18 |

* Due to consecutive days with disease resolution and followed by a day with no disease resolution as the last assessment.

**Due to consecutive days with no disease resolution occur after days with disease resolution.

DR = disease resolution. N=no; Y=yes. NA=Not available.

For time to disease resolution, a stratified 1-sided log-rank test, stratified by number of days since onset of symptoms at time of randomization (<6 days or ≥6 days), will be used to compare between the study intervention and control. The Kaplan-Meier method will be used to obtain the estimates of medians with the associated 2-sided 95% CIs of time to disease resolution,

computed using Brookmeyer and Crowley method. A stratified Cox proportional hazards model, stratified by number of days since onset of symptoms at time of randomization (<6 days or ≥ 6 days) will be used to estimate the hazard ratio and the corresponding 2-sided 95% CI associated with the rate of disease resolution for the study intervention relative to control.

Due to anticipated heterogeneity in the rate of disease resolution, pre-specified baseline variables, including age and BMI will be included in the model to increase precision. Including time-dependent variables, i.e., log(time)-by-variables interactions, to the model to fit a stratified Cox non-proportional hazards model to assess the proportional hazards assumption. If the coefficients for the time-dependent variables are not statistically different from zero based on a chi-square test with 1 degree of freedom would suggest that proportional hazards assumption is adequate for all variables included in the model.

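### SAP 7.1 uses one final efficacy set for every endpoint, so ongoing, event-free participants drop out of the Day 8, Day 14 and time-to-resolution analyses while early progressors and discontinuers stay in

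*SAP*

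**What the plan says.** SAP 7.1 admits a participant to the final efficacy set under either of two limbs. The first is "Completed or discontinued the study or progressed prior to 5 February, 2021", which can be met at any study day. The second is "Completed Day 21 or later visits as of 5 February, 2021".

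The set governs every efficacy analysis: "Efficacy analyses will be produced for randomized participants who meet the selection criteria described above and also meet the analysis population criteria described below". Table 2 defines the ITT population as "All participants in the ITT population who met the criteria stated above" and draws the mITT and PP populations from it. SAP 11.2 adds: "Secondary analyses will be conducted in the ITT population". No early-day or time-to-event endpoint has a rule of its own.

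Two reasons are given. SAP 4 says: "To address potential for substantial under-estimation of the treatment effect, efficacy analyses will be performed on a final efficacy analysis population". SAP 7.1 adds that the stop affects the evaluation of participants who had not reached Day 21 by 4 February. SAP 4 also ends efficacy assessments for those participants from that date.

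Several secondary endpoints are read earlier than Day 21. Progression is listed in SAP 5 as "Gates MRI ordinal scale ≥ 3) at Days 8, 14 and 21". Symptom resolution, the two ordinal scales and hospitalization are also read at Days 8 and 14. SAP 11.2.2.1 tests the time-to-event endpoint as follows: "For time to disease resolution, a stratified 1-sided log-rank test", with Kaplan-Meier and Cox estimates.

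**The concern.** Dilution is a sound reason to be wary of a Day 28 outcome in someone whose treatment was cut short. It is no reason to discard a Day 8 or Day 14 assessment made before dosing ended. The restriction is therefore wider than its rationale.

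The loss is also not neutral. Among participants first dosed in the last three weeks, someone who progressed or discontinued enters the set through the first limb, while someone still under observation and event-free does not. At Days 8 and 14 this raises the progression proportions in both arms. It will tend to lower the resolution proportions, since the late entrants who remain are mainly those who did badly or left. At stake are the precision and the interpretability of the secondary analyses.

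**Working it through.** **Dates.** SAP 9.2 sets study day = date − Day 1 date + 1. The latest first-dose date that puts a given study day on 4 February is:

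- Day 21: 15 January
- Day 14: 22 January
- Day 8: 28 January

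First doses from 16 January to 4 February (20 calendar days) were below Day 21 at the stop. Of these days, 16–28 January (13 days) allowed Day 8 to be reached and 16–22 January (7 days) allowed Day 14.

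**Enrolment (assumed).** Day 28 on the 8 January interim cut means a first dose by 12 December, so I take 200 first dosed by then. Protocol 13.2 expected 600 enrolled by the cut for the second interim, previously planned at about 400 completing Day 28. That implies about 200 in 28 days, or 7 a day. I use r = 3 to 7 a day; the lower value is only an assumption. From 13 December to 15 January is 34 days, so the base past Day 21 is 200 + 34r = 302 to 438.

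**Upper limit on participants added back.** Day 8: 13r = 39 to 91. Day 14: 7r = 21 to 49. If assessments due on 4 February itself were not made, the windows shrink to 12 and 6 days: 36 to 84 and 18 to 42.

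**Gross precision.** SE ratio = √[base/(base + added)].

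- Day 8: √(302/341) = 0.941 and √(438/529) = 0.910, a reduction of 5.9 to 9.0%
- Day 14: √(302/323) = 0.967 and √(438/487) = 0.948, a reduction of 3.3 to 5.2%

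**Net of those already kept.** Take pooled progression as (30% + 19.5%)/2 = 24.75%, using the SAP 9.1.1 rates, and assume it accrues linearly to Day 14. (The 294 per group in that section reproduces: 264 evaluable/0.9 = 294. It is not in dispute.)

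- Day 8 window (study days 8 to 20 at the stop): kept progressors = r × 0.2475 × (63/14 + 7) = 2.85r = 8.5 to 19.9. Net added = 30.5 to 71.1. SE ratio = √(310.5/341) = 0.954 and √(457.9/529) = 0.930, a reduction of 4.6 to 7.0%.
- Day 14 window: kept progressors = r × 0.2475 × 7 = 1.73r = 5.2 to 12.1. Net added = 15.8 to 36.9. SE ratio = √(307.2/323) = 0.975 and √(450.1/487) = 0.961, a reduction of 2.5 to 3.9%.

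Kept discontinuers would lower these a little further.

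**Larger base.** SAP 7.1 describes the interim as using the first 200 who qualified, so more may have done so. With 300 by 12 December, the same steps give about 3.5 to 6% at Day 8 and 2 to 3% at Day 14.

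**Selection (illustration only).** Assume 200 per arm past Day 21, true progression 30% versus 19.5% accruing linearly to Day 14, 2 to 7 first doses a day over both arms, and only progressors kept among late entrants:

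| | True | Under SAP 7.1 |
|---|---|---|
| Control, Day 8 | 17.1% | 18.2 to 20.6% |
| Control, Day 14 | 30.0% | 31.4 to 34.6% |
| Risk difference, Day 8 | −6.0 points | −6.3 to −6.9 |
| Risk difference, Day 14 | −10.5 points | −10.8 to −11.6 |

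**The case against.** Four arguments for the plan deserve weight.

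**The rule has two limbs.** A reader who stops at the Day 21 line might infer that SAP 7.1 demands Day 21 of everyone. It does not, because participants below Day 21 who progressed or discontinued are kept. The gross counts are therefore upper limits. The same limb is what makes the exclusion depend on outcome, so this corrects the description and adds to the problem.

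**Time-to-resolution data below Day 21 are not complete.** A reader might infer that they are, and that standard survival methods simply absorb the stop. The endpoint runs through Day 28, and Table 3 dates the event from the start of the last resolved sequence. In Table 4, Participants 8 and 12 resolve at Day 12 and are later counted as unresolved. Participants below Day 21 had no symptom assessments after the stop, so their resolutions are provisional. This objection stands. The data are still usable, since Table 3 already accepts provisional resolutions from participants who discontinue, and SAP 11.2.2.2 already censors at the last visit those past Day 21 without two consecutive negative tests at the stop. I give no figure for the gain in resolution events, because any such figure would treat provisional resolutions as final.

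**A common population has value.** One set for all endpoints is simpler to report. That is true, but it does not justify outcome-dependent entry.

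**The gain is small.** It is a few per cent of the standard error on secondary endpoints in a trial already stopped for futility. This is fair, and it limits the weight of the point.

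**Conclusion.** The concern holds in this form: one efficacy set, with no exception by endpoint, removes ongoing, event-free participants from the Day 8, Day 14 and time-to-resolution analyses. For Days 8 and 14, the stated reason does not reach assessments made before 4 February, and the exclusion selects on outcome. For time to resolution, partial data that the SAP's own rules could handle are left out.

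The size is modest: a standard error lower by roughly 4 to 7% at Day 8 and 2 to 4% at Day 14, and less with a larger base. These figures rest on assumed enrolment and an assumed progression curve, because the documents do not report how many participants were below Day 21 at the stop. They should not be read as a known count of lost participants. The shift in the risk difference is likewise an illustration. Under that model, if progression were the same in both arms, both proportions would rise alike.

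A reader might also infer that the primary Day 28 analysis is wrong on this ground. It is not: participants below Day 21 had no efficacy follow-up to Day 28, so this loss of early data does not arise there. The outcome-dependent limb does act at Days 21 and 28, but that needs its own correction.

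**What to change.** In SAP 7.1, define the efficacy set by endpoint.

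- **Day 8 and Day 14 analyses.** Include all randomized participants whose first-dose date (randomization date if undosed) allowed that day to be reached before the stop, whatever their outcome. The cut-off is 27 January 2021 for Day 8 and 21 January for Day 14, or 28 and 22 January if assessments due on 4 February itself were made. State which applies.
- **Both time-to-resolution analyses.** Include all randomized participants. For those below Day 21 at the stop, apply the Table 3 rule for discontinued participants: an event, dated as in Table 3, if resolved at the last assessment on or before 4 February; otherwise censored at that assessment. Note in the report that these resolutions are provisional.
- **Progression days.** SAP 11.2.4 names Days 8, 12 and 21, whereas SAP 5 and SAP 11 name Days 8, 14 and 21. Reconcile these, since otherwise the Day 14 rule has no matching progression analysis.
- **Days 21 and 28.** Correct the outcome-dependent limb separately; this change does not remove it there.

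The cost is SAP wording and a little programming, with no new data. The downside is that N differs by endpoint, which needs a table footnote.

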7.2 Assigning Shared Controls across Multiple Intervention-specific Analysis Populations

Each intervention may be initiated and stopped at different time frames, and within different sites. Depending on the number of interventions that a participant can be eligible to receive, a participant randomized to a control arm may be part of multiple intervention-specific analysis populations for the purposes of comparing a single intervention to control. We note the following core principles associated with sharing controls across intervention-specific analysis populations:

- Controls will only be shared across multiple intervention-specific populations when there is randomization across those interventions and the control. All participants will only be randomized once.
- A participant who is eligible for multiple interventions at a site will be randomized equally to receive 1 of the interventions for which they are eligible vs control. Participants randomized to control will be equally likely to receive the matched control of each intervention for which they are eligible. If the participant is randomized to control, they will be assigned to each of the intervention-specific analysis populations included in the randomization. A participant randomized to control will not be assigned to an intervention-specific analysis population that was not included in the randomization.
- Controls will only be shared contemporaneously. A participant can only be used in the intervention-specific population(s) that was available and included at the time of their randomization.
- A control does not have to receive the intervention-specific matched control to be eligible for an intervention-specific population. For example, a participant randomized 1:1:1 to receive 2 available interventions vs control would serve as a control for each of the interventions regardless of the matched control assigned. The primary comparison will utilize eligible participants in the intervention-specific analysis population randomized to control, regardless of the specific intervention-specific matched control that was randomized.

The randomization strategy for up to 3 contemporaneously available interventions is shown in Figure 1. Strategies for 2 interventions and for 1 intervention are shown in Figure 2 and Figure 3, respectively.

This randomization strategy can easily be generalized beyond 3 contemporaneously available interventions and will ensure approximately equal randomization of each intervention to control, while helping to maintain blinding and minimize possible bias.

Participants randomized to rivaroxaban or control under the principles listed above will be assigned to the rivaroxaban-specific analysis population.

Figure 1: Randomization for sites where 3 interventions are being studied

[figure not shown]

Figure 2: Randomization strategy for sites where 2 interventions are being studied

[figure not shown]
[figure not shown]

Figure 3: Randomization strategy for sites where only 1 intervention is being studied

8 CHANGES IN CONDUCT OR PLANNED ANALYSES FROM THE PROTOCOL

Not applicable.

9 OVERALL STATISTICAL CONSIDERATIONS

9.1 Determination of Sample Size

9.1.1 Efficacy

The total number of participants planned to be enrolled is approximately 600 (300 per group). If the true control rate for progression to moderate or severe category or greater is at least 30%, 294 participants per group will result in 80% power when the true study intervention effect is 35% as a relative decrease of rate progression, i.e., a true rivaroxaban rate of progression of 19.5% is 35% lower than that of a true placebo-control rate of progression of 30%. This sample size accounts for a drop-out rate of 10% and a 1-sided Type I error rate of 2.5%. To account for one planned interim futility analysis without adversely affecting the statistical power, the sample size was increased to 300 per group.

9.1.2 Safety

With 300 participants in the rivaroxaban intervention group, there is 80% probability to observe at least 1 SAE related to rivaroxaban when the true SAE rate is at least 0.54%.

9.2 General Conventions

Frequency (n) and percentages (%) will be used to summarize categorical variables; mean, standard deviation (SD), median, minimum, and maximum will be used to summarize continuous variables.

Decimal precision for summary statistics of continuous variables will be based on the mean value. Typically, the mean will contain 1 more decimal place than actual values but the decimal precision may vary in order to obtain an organized and understandable table or listing. The median will contain the same number of decimal places as the mean, the SD will contain 1 more decimal place than the mean, and the minimum and maximum will contain 1 less decimal place than the mean.

Unless otherwise specified, the denominators for percentages will be the number of participants in each intervention group with non-missing data for the variable of interest.

The day of receiving first dose of study intervention is defined as Study Day 1 or Day 1. All other study days will be computed relative to Day 1. For events on or after Day 1, study day for a particular event or visit will be calculated as $\text{Date}_{\text{event}} - \text{Date}_{\text{Day 1}} + 1$. For events before Day 1, study day for a particular event will be calculated as $\text{Date}_{\text{event}} - \text{Date}_{\text{Day 1}}$. Day 0 will not be used.

9.3 Baseline definition

Unless otherwise specified, Baseline is defined as the last non-missing assessment (scheduled or unscheduled) prior to the first dose. In the case where the last non-missing assessment and the first dose coincide (i.e., assessments on Day 1), that assessment will be considered pre-intervention (Baseline).

9.4 Stratification Factor

The variable associated with the stratification factor of number of days since onset of symptoms at time of randomization [original protocol (<3 days or ≥ 3 days); protocol amendment 1 (<6 days or ≥ 6 days)] will be defined according to data from the IVRS/IWRS. If there are any participants who are identified as being miss-stratified (i.e. randomized to the incorrect strata), a sensitivity analysis of the primary analysis will be carried out using the derived stratification variable for number of days since onset of symptoms at time of randomization. As discussed in section 6 participants enrolled under the original strata will be analyzed under the derived stratification variable for number of days since onset of symptoms at time of randomization (<6 days or ≥ 6 days).

9.5 Handling of Missing Data

Missing and partial dates of prior and concomitant medications and adverse events will be imputed to determine the relationship between the start date of the event and the first dose date of study drug. The imputation rules provided in Appendices 2 and 3.

Statistical methods to address missing data for efficacy endpoints are provided in Section 11.

9.6 Pooling Strategy for Study Sites

Randomization will be stratified by site. Generally, all sites will be pooled by intervention for analysis purposes. Summaries by site will be included for relevant endpoints. Details are provided in the relevant sections.

9.7 Visit Windows/Unscheduled Visits

Visit windowing in general will not be applied. Unscheduled visits will not be included in by-visit summaries or analysis, but may contribute to the Baseline value and worst post-baseline assessments. In the case of a retest (same visit number assigned), the latest available test result as provided in the data transfer for that visit/time point will be used for by-visit summaries.

